5.0 DOSAGES AND DISPENSATION OF DRUGS

5.1 FFX Administration

The study drugs are defined as 5-FU, LV, oxaliplatin, and irinotecan (FFX). Due to the infusional 5-FU, study drugs must be administered via central line (mediport, PICC, or other). Treatment cycles are every 14 days \pm 3 days (except for C6 which is 28 days in DL1 and 21 days in DL2). The study drug dosages and administration are only recommended – dosages and supportive medication can be modified at the discretion of the investigator, taking into consideration dose modifications during cycles 1-5. Per the PRODIGE 24 trial, the 5-FU bolus is omitted and irinotecan is 150 mg/m². A research infusion nurse will access the patient's line. Treatment will then be administered in the following order (substitutions for prophylactic medications are allowed at the treating investigator's discretion):

Table 5. Drug Administration

Drug	Indication	Dose/Route	Duration
Fosaprepitant	Nausea prophylaxis	150 mg IV	30 minutes
Ondansetron	Nausea prophylaxis	16 mg IV	15 minutes
Dexamethasone	Nausea prophylaxis	10 mg IV	15 minutes
Leucovorin	Treatment	400 mg/m ² IV	60 minutes
Oxaliplatin	Treatment	85 mg/m ² IV	120 minutes (can be administered simultaneously with leucovorin via a Y-connector)
Atropine	Diarrhea prophylaxis	0.5 mg IV	IV push
Irinotecan	Treatment	150 mg/m ² IV	90 minutes
5-fluorouracil	Treatment	2400 mg/m ² IV	46 hours (continuous infusion)
Pegfilgrastim on-pro	Growth factor support	6 mg SC	Administered on day 3 (after 5-fluorouracil pump is unhooked)

The patient will return to the research infusion clinic after 46 hours for disconnection of the 5-FU infusional pump and administration of pegfilgrastim on-pro. Use of growth factor support is highly recommended but is at the discretion of the investigator. Alternatively, pegfilgrastim 6 mg SC can be administered on day 4 (if not using on-pro administration).

5.2 Packaging, Labeling, Storage, and Handling of Chemotherapy

5-FU, LV, oxaliplatin, and irinotecan should be stored and handled as per their respective FDA labels and following protocols and guidelines of LCCC (see <http://www.osha.gov/SLTC/hazardousdrugs/index.html>).^{18-20,23}

5.3 Proton Beam Therapy

PRT planning will commence following the screening visit with the radiation oncologist. PRT volumes will include a clinical target volume of the highest at risk nodal regions: celiac, SMA, and para-aortic regions. The porta hepatic nodes have been shown to be at significantly less risk for local recurrence and will not be included in the treatment.^{29,30} The normal tissue constraints are as follows: stomach and small bowel: V30 < 0.1 cc, V20 < 5 cc, V15 < 10 cc, cord D_{max} < 25 Gy, liver V17 < 33%. Target volume coverage should be greater than 95%. Two posterior oblique beams or 1 posterior and 1 lateral beam are encouraged. The radiation oncology study chair will approve of all treatment plans.

If PRT has started and becomes unavailable, it will restart when available and the patient will resume the treatment schedule following this delay. If greater than 14 days elapse after PRT is held, PRT will not be completed and the patient will resume standard adjuvant mFOLFIRINOX for remainder of treatment.

6.0 SAFETY VARIABLES AND TOXICITY ASSESSMENT

The Principal Investigator or sub-investigators will assess adverse events, laboratory data and vital signs throughout the study. Adverse events will be assessed by NCI CTCAE Version 5.0: https://ctep.cancer.gov/protocolDevelopment/electronic_applications/docs/CTCAE_v5_Quick_Reference_8.5x11.pdf.

6.1 Adverse Event Assessment

The investigators will monitor each subject for clinical and laboratory evidence of adverse events on a routine basis throughout the study. The investigator will assess and record any adverse event in detail including the date of onset, event diagnosis (if known) or sign/symptom, severity, time course, duration and outcome, relationship of the adverse event to study drug, and any action(s) taken. For serious adverse events not considered “probably related” to study drug, the investigator will provide an “Other” cause of the event. For adverse events to be considered intermittent, the events must be of similar nature and severity. Adverse events, whether in response to a query, observed by personnel, or reported spontaneously by the subject will be recorded. All adverse events will be followed to a satisfactory conclusion.

6.2 Study Monitoring

6.2.1 Data Safety Monitoring Committee at Georgetown

The Georgetown Lombardi Comprehensive Cancer Center will be responsible for the data and safety monitoring of this multi-site trial. As this study is an investigator initiated study phase I study, it is considered a high-risk study which requires real-time monitoring by the PI and study team and review every 4 months by the LCCC Data and Safety Monitoring Committee (DSMC).

The Principal Investigator and the Co-Investigators will review the data including safety monitoring at their weekly institution based disease group meetings, on monthly disease group teleconferences, and monthly teleconferences between study sites.

All Severe Adverse Events (SAEs) are required to be reported to the IRB. Based on SAEs, the IRB retains the authority to suspend further accrual pending more detailed reporting and/or modifications to further reduce risk and maximize the safety of participating patients.

Progress on the trial and the toxicities experienced will be reviewed by the LCCC Data and Safety Monitoring Committee every 4 months from the time the first patient is enrolled on the study. Results of the DSMC meetings will be forwarded to the IRB with recommendations regarding need for study closure.

DSMC recommendations should be based not only on results for the trial being monitored as well as on data available to the DSMC from other studies. It is the responsibility of the PI to ensure that the DSMC is kept apprised of non-confidential results from related studies that become available. It is the responsibility of the DSMC to determine the extent to which this information is relevant to its decisions related to the specific trial being monitored.

A written copy of the DSMC recommendations will be given to the trial PI and the IRB. If the DSMC recommends a study change for patient safety or efficacy reasons the trial PI must act to implement the change as expeditiously as possible. In the unlikely event that the trial PI does not concur with the DSMC recommendations, then the LCCC Associate Director of Clinical Research must be informed of the reason for the disagreement. The trial PI, DSMC Chair, and the LCCC AD for Clinical Research will be responsible for reaching a mutually acceptable decision about the study and providing details of that decision to the IRB. Confidentiality must be preserved during these discussions. However, in some cases, relevant data may be shared

with other selected trial investigators and staff to seek advice to assist in reaching a mutually acceptable decision.

If a recommendation is made to change a trial for reasons other than patient safety or efficacy the DSMC will provide an adequate rationale for its decision. If the DSMC recommends that the trial be closed for any reason, the recommendation will be reviewed by the Associate Director for Clinical Research at G-LCCC. Authority to close a trial for safety reasons lies with the IRB, with the above described input from DSMC and the AD for Clinical Research.

6.3 Adverse Event and Toxicity Definitions

6.3.1 Adverse Event

An adverse event (AE) is defined as any untoward medical occurrence in a patient or clinical investigation subject administered a pharmaceutical product and which does not necessarily have a causal relationship with this treatment. An adverse event can therefore be any unfavorable and unintended sign (including an abnormal laboratory finding), symptom, or disease temporally associated with the use of a medicinal (investigational) product, whether or not the event is considered causally related to the use of the product. Such an event can result from use of the drug as stipulated in the protocol or labeling, as well as from accidental or intentional overdose, drug abuse, or drug withdrawal. Any worsening of a pre-existing condition or illness is considered an adverse event. Laboratory abnormalities and changes in vital signs are considered to be adverse events only if they result in discontinuation from the study, necessitate therapeutic medical intervention, and/or if the investigator considers them to be adverse events.

An elective surgery/procedure scheduled to occur during a study will not be considered an adverse event if the surgery/procedure is being performed for a pre-existing condition and the surgery/procedure has been pre-planned prior to study entry. However, if the pre-existing condition deteriorates unexpectedly during the study (e.g., surgery performed earlier than planned), then the deterioration of the condition for which the elective surgery/procedure is being done will be considered an adverse event.

6.3.2 Serious Adverse Events

If an adverse event meets any of the following criteria, it is to be reported to the DSMC as a serious adverse event (SAE) within 24 hours of the study personnel being made aware of the serious adverse event.

- 1) **Death of Subject** An event that results in the death of a subject.
- 2) **Life-Threatening** An event that, in the opinion of the investigator, would have resulted in immediate fatality if medical intervention had not been taken. This does not include an event that would have been fatal if it had occurred in a more severe form.
- 3) **Hospitalization or**
- 4) **Prolongation of Hospitalization** An event that results in an admission to the hospital for any length of time or prolongs the subject's hospital stay. This does not include an emergency room visit or admission to an outpatient facility.
- 5) **Congenital Anomaly** An anomaly detected at or after birth, or any anomaly that results in fetal loss.
- 6) **Persistent or Significant Disability/Incapacity** An event that results in a condition that substantially interferes with the activities of daily living of a study subject. Disability is not intended to include experiences of relatively minor medical significance such as headache, nausea, vomiting, diarrhea, influenza, and accidental trauma (e.g., sprained ankle).
- 7) **Important Medical Event Requiring Medical or Surgical Intervention to Prevent Serious Outcome** An important medical event that may not be immediately life-threatening or result in death or hospitalization, but based on medical judgment may

jeopardize the subject and may require medical or surgical intervention to prevent any of the outcomes listed above (i.e., death of subject, life-threatening, hospitalization, prolongation of hospitalization, congenital anomaly, or persistent or significant disability/incapacity). Examples of such events include allergic bronchospasm requiring intensive treatment in an emergency room or at home, blood dyscrasias or convulsions that do not result in inpatient hospitalization, or the development of drug dependency or drug abuse.

- 8) **Spontaneous Abortion** Miscarriage experienced by study subject.
- 9) **Elective Abortion** Elective abortion performed on study subject.

6.3.3 Adverse Event Severity

The study investigator will rate the severity of each adverse event according to the NCI CTCAE Version 5.0. For adverse events not captured by the NCI CTCAE Version 5.0, the following should be used:

- 1) **Grade 1 (Mild)** The adverse event is transient and easily tolerated by the subject.
- 2) **Grade 2 (Moderate)** The adverse event causes the subject discomfort and interrupts the subject's usual activities.
- 3) **Grade 3-4 (Severe or Life Threatening)** The adverse event causes considerable interference with the subject's usual activities and may be incapacitating or life-threatening.
- 4) **Grade 5 (Death)** The adverse event resulted in death of the subject.

6.3.4 Relationship to Study Drug

The investigator will use the following definitions to assess the relationship of the adverse event to the use of study drug:

- 1) **Definitely Related** An adverse has a clear temporal relationship to study drug and/or recurs on re-challenge and an Other cause of event is extremely unlikely.
- 2) **Probably Related** An adverse event has a strong temporal relationship to study drug or recurs on re-challenge and an Other cause of event is unlikely or significantly less likely.
- 3) **Possibly Related** An adverse event has a strong temporal relationship to the study drug and an Other cause of event is equally or less likely compared to the potential relationship to study drug.
- 4) **Probably Not Related** An adverse event has little or no temporal relationship to the study drug and/or a more likely Other cause of event exists.
- 5) **Not Related** An adverse event is due to an underlying or concurrent illness or effect of another drug and is not related to the study drug (e.g., has no temporal relationship to study drug or has a much more likely Other cause of event).

If an investigator's opinion of possibly, probably not, or not related to study drug is given, an Other cause of event must be provided by the investigator for the serious adverse event.

6.4 Adverse Event Collection Period

All adverse events reported from the time of study drug administration until 30 days following discontinuation of study drug administration have elapsed will be collected, whether elicited or spontaneously reported by the subject. In addition, serious adverse events will be collected from the time the subject signed the study-specific informed consent.

6.5 Adverse Event Reporting

In the event of a serious adverse event, whether related to study drug, study procedure such as a biopsy, or even if not directly related to any study intervention, the investigator will notify the IRB within 72 hours of being made aware of the serious adverse event.

The SAE report should comprise a full written summary, detailing relevant aspects of the adverse events in question. Where applicable, information from relevant hospital case records and autopsy reports should be included.

6.6 Pregnancy

In the event of a positive pregnancy test result, study drugs will be immediately discontinued. The investigator must report the positive pregnancy test within 72 hours of the study personnel becoming aware of the pregnancy to the IRB. Patients should also notify the investigator if it is determined after completion of the study that they become pregnant either during the treatment phase of the study or within five days after the treatment period. Information regarding a pregnancy occurrence in a study subject and the outcome of the pregnancy will be collected, and the status of the mother and child should be reported to the IRB after delivery. Pregnancy in a study subject is not considered an adverse event but does require discontinuation of the subject from the study. However, the medical outcome of an elective or a spontaneous abortion, stillbirth or congenital anomaly is considered a serious adverse event and must be reported to the IRB within 72 hours of study personnel becoming aware of the event. Male subjects should also notify the investigators if the subject's partner should become pregnant during the study, this should also be reported within 72 hours of study personnel awareness.

6.7 Toxicity Management and Dose Adjustments

6.7.1 Dose Reduction and Delays of FFX

As patients will enter the study already having completed 5 cycles of FFX, discretion is given to the investigator to continue patients at the same doses as cycle 5. Therefore, all dose modifications are recommended but left to the discretion of the investigator.

Table 6. Dose Levels for Modifications for FFX (Recommended)

Episode #	Irinotecan	Oxaliplatin	5-FU/LV
1 st	Decrease to 120 mg/m ²	Decrease to 75 mg/m ²	Decrease to 1800 mg/m ²
2 nd	Decrease to 90 mg/m ²	Decrease to 65 mg/m ²	Decrease to 1200 mg/m ²
3 rd	Off Study	Off Study	Off Study

Table 7. Dose Modifications for FFX (Recommended)

Toxicity	Instruction
ANC < 1500/mm ³	Hold until ANC ≥ 1500/mm ³ and reduce one dose level as above
Platelets < 75000/mm ³	Hold until platelets ≥ 75000/mm ³ and reduce one dose level as above
Febrile neutropenia or Grade 4 neutropenia ≥ 7 days	Hold until afebrile and ANC ≥ 1500/mm ³ , reduce one dose level as above
Grade 3-4 diarrhea	Initiate Imodium prn, hold until resolved to baseline or grade 1, reduce one dose level as above
Grade 3-4 peripheral neuropathy	Discontinue oxaliplatin

Other grade 3-4 toxicity	Hold until toxicity resolves to baseline or grade 1, reduce one dose level as above
--------------------------	---

6.8 Prohibited Concurrent Medications

The following medications must be discontinued at least 2 weeks prior to C6D1 (strong CYP3A4 inhibitors or inducers, strong UGT1A1 inhibitors):

Atazanavir, Atazanavir/ritonavir, boceprevir, clarithromycin, cobicistat, conivaptan, danoprevir/ritonavir, darunavir/ritonavir, elvitegravir/ritonavir, grapefruit juice, idelalisib, indinavir, indinavir/ritonavir, itraconazole, ketoconazole, lopinavir/ritonavir, mibefradil, nefazodone, nelfinavir, ombitasvir/paritaprevir/dasabuvir/ritonavir (VIEKIRA PAK), posaconazole, ritonavir, saquinavir/ritonavir, telaprevir, telithromycin, tipranavir/ritonavir, troleandomycin/voriconazole, carbamazepine, enzalutamide, lumacaftor, mitotane, phenobarbital, phenytoin, rifabutin, rifampin (rifampicin), St. John's wort (*hypericum perforatum*), adenine, propofol, indomethacin, nilotinib, pazopanib, regorafenib, flunitrazepam, erlotinib, sorafenib, enasidenib, pibrentasvir, glecaprevir, rucaparib, ertugliflozin, fostamatinib, dolutegravir, valproic acid, flurbiprofen, eltrombopag, silibinin A, and sodium aurothiomalate.

7.0 EFFICACY ASSESSMENT

7.1 Efficacy Variables

Disease recurrence will be assessed by a CT scan (or other appropriate modalities such as by way of MRI consistent with the modality used prior to treatment) utilizing RECIST v1.1 criteria. Assessments will be performed within 2 months of C6D1, at EOT, and at follow-up visits.

We will track the success rate in screening patients, completion of PRT planning, completion of proton beam treatment, and completion of adjuvant therapy (including number of cycles completed and relative dose intensity).

7.2 RECIST v1.1 Criteria for Tumor Response

Changes in the measurable lesions over the course of therapy will be evaluated using the RECIST v1.1 criteria.

7.2.1 Definition of Lesions

7.2.1.1 Measurable Disease

The presence of at least one measurable lesion. If the measurable disease is restricted to a solitary lesion, its neoplastic nature should be confirmed by cytology/histology.

7.2.1.2 Measurable Lesions

Lesions that can be accurately measured in at least one dimension with longest diameter ≥ 20 mm using conventional techniques or ≥ 10 mm with CT scan.

7.2.1.3 Non-measurable Lesions

All other lesions, including small lesions (longest diameter < 20 mm with conventional techniques or < 10 mm with a CT scan), bone lesions, leptomeningeal disease, ascites, pleural/pericardial effusion, inflammatory breast disease, lymphangitis cutis/pulmonis, cystic lesions and also abdominal masses that are suspicious though may or may not be confirmed and followed by imaging techniques.

All measurements should be taken and recorded in metric notation, using a ruler or calipers. All baseline evaluations should be performed as closely as possible to the beginning of treatment and never more than 14 days before the beginning of the treatment. The same method of assessment and the same technique should be used to characterize each identified and reported lesion at baseline and during follow-up. Clinical lesions will only be considered measurable when they are superficial (e.g., skin nodules and palpable lymph nodes). For the case of skin lesions, documentation by color photography including a ruler to estimate the size of the lesion is required.

7.2.2 Methods of Measurement

CT and MRI are the best currently available and reproducible methods to measure target lesions selected for response assessment. Conventional CT and MRI should be performed with cuts of 10 mm or less in slice thickness contiguously. Spiral CT should be performed using a 5 mm contiguous reconstruction algorithm. This applies to tumors of the chest, abdomen and pelvis. For accurate objective response evaluation, ultrasound should not be used to measure tumor lesions. However, ultrasound is a possible alternative to clinical measurements of superficial palpable lymph nodes, subcutaneous lesions and thyroid nodules. Ultrasound might also be useful to confirm the complete disappearance of superficial lesions usually assessed by clinical examination. Cytology and histology can be used to differentiate between PR and CR in rare cases (e.g., after treatment to differentiate between residual benign lesions and residual malignant lesions in tumor types such as germ cell tumors).

7.3 Definition of Disease Recurrence

Disease progression will be defined as:

- 1) Radiologic progression of disease by RECIST v1.1 criteria.
- 2) Clinical progression as determined by the investigator, which may be characterized as, but is not limited to:
 - a. Increase of at least 2 points in ECOG performance status attributable to cancer progression.
 - b. Requirement for radiation (beyond palliative radiation for bone pain relief as outlined in 3.4.3.3), chemotherapy or surgery.
- 3) Death from disease progression

8.0 STATISTICAL CONSIDERATIONS

8.1 Primary Objective:

To determine the recommended phase II dose and schedule (RP2D) of short-course PRT integrated within adjuvant FFX (radiation 12 days following chemotherapy or 5 days following chemotherapy) for resected PDAC. The co-primary objectives are to demonstrate the safety and feasibility of short short-course proton radiation within systemic adjuvant chemotherapy with FFX, including the number of cycles received and relative chemotherapy dose-intensity.

8.2 Exploratory Objectives:

To determine, in patients with resected PDAC undergoing PRT integrated within adjuvant FFX:

8.2.1 Median recurrence-free survival (mPFS)

8.2.2 Median overall survival (mOS)

8.3 Primary Endpoint:

The primary endpoint is to determine the RP2D between the 2 proposed schedules. Using a 3+3 dose-escalation schema, 2-12 patients will be required to determine the RP2D.

Co-primary endpoints:

8.3.1 Safety: adverse event data will be collected and presented as descriptive statistics using the CTCAE version 5.0.

8.3.2 Feasibility: we will track the success rate in screening patients, completion of proton beam planning, completion of proton beam treatment, and completion of adjuvant therapy (including number of cycles completed and relative dose intensity).

8.4 Exploratory Endpoints:

8.4.1 Recurrence-free survival (RFS), defined as time from surgery until evidence of disease recurrence.

8.4.2 Overall survival (OS), defined as time from surgery until death from any cause or last follow-up.

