HIV	Human immunodeficiency virus
HR	Hazard ratio
IFL	Irinotecan, fluorouracil (bolus), and leucovorin
IHC	Immunohistochemistry
IND	Investigational new drug
INR	International normalized ratio
IV	Intravenously
LCCC	Lombardi Comprehensive Cancer Center
LD	Longest diameter
LFT	Liver profile
LLN	Lower limit of normal
LV	Leucovorin
MRI	Magnetic resonance imaging
mOS	Median overall survival
mPFS	Median progression-free survival
NGS	Next-generation Sequencing
ORR	Overall response rate
OS	Overall survival
PCR	Polymerase chain reaction
PD	Progression of disease
PI	Principal investigator
PK	Pharmacokinetics

PO	By mouth
PR	Partial response
PRT	Proton Radiation Therapy
PS	Performance Status
PT	Prothrombin time
PTT	Partial thromboplastin time
QD	Once daily
RECIST	Response Evaluation Criteria in Solid Tumors
RFS	Recurrence-free survival
RNA	Ribonucleic acid
RP2D	Recommended Phase II Dose
RR	Response rate
SAE	Significant adverse event
SD	Stable disease
TS	Thymidylate synthase
UGT1A1	UDP glucuronosyltransferase family 1 member A1
ULN	Upper limit of normal

[figure not shown]
STUDY SYNOPSIS

Title	Phase I Study of Proton Therapy in Adjuvant Pancreatic Cancer (PROTON-PANC)
Short Title	Proton Therapy in Adjuvant Pancreatic Cancer
Protocol Number	2018-1021
Clinicaltrials.gov number:	pending
Phase	Phase I
Investigational Agents	1) Proton Beam Therapy
Indication	Resected adenocarcinoma of the pancreatic head

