Objectives	
Primary Objective:
 
To determine the recommended phase II dose and schedule (RP2D) of short-course PRT integrated within adjuvant FFX (radiation 12 days following chemotherapy or 5 days following chemotherapy). The co-primary objectives are to demonstrate the safety and feasibility of short-course PRT within systemic adjuvant chemotherapy with FFX, including the number of cycles received and relative chemotherapy dose-intensity.
 
Exploratory Objectives:
 
To determine the median recurrence-free survival (mRFS) and median overall survival (mOS) in patients treated with adjuvant FFX and proton radiation.

Number of Subjects	A minimum of 2 and a maximum of 12 evaluable patients

Diagnosis and Main Inclusion and Exclusion Criteria
	
Key Inclusion Criteria
 
 • Pathologically-confirmed pancreatic adenocarcinoma of the pancreatic head • Undergone pancreaticoduodenectomy with curative intent • Completed 2 cycles of adjuvant chemotherapy composed of 5-fluorouracil, leucovorin, oxaliplatin, and irinotecan • Complete resection (R0) or resection with microscopic positive margins (R1) • Adequate healing post-operatively • Adequate hepatic, renal, and bone marrow function • Eastern Cooperative Oncology Group (ECOG) Performance Status (PS) of 0-1 • Prior neoadjuvant chemotherapy is allowed 
Key Exclusion Criteria
 
 • Ampullary adenocarcinoma • Woman who are pregnant or breastfeeding • Macroscopic positive margins (R2) or evidence of residual local or metastatic disease • Resection not including pancreaticoduodenectomy • Known allergy or intolerance to leucovorin, 5-fluorouracil, oxaliplatin, or irinotecan • Prior radiation to the upper abdomen • Inability to swallow pills or bowel obstruction • Any invasive cancer in the previous 3 years requiring chemotherapy or radiation or anticancer therapy following surgery • Insurance unwilling to pre-authorize PRT, FFX, and pegfilgrastim • Clinically significant liver disease 
 ○ Patients with resolved hepatitis B infection are eligible if HBsAg testing is negative ○ Patients with resolved hepatitis C infection are eligible if viral RNA PCR is negative • Uncontrolled HIV infection (CD4 count must be at least 200 and viral load undetectable on a stable antiretroviral regimen) • Major surgery within 4 weeks prior to enrollment

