8.6 Analytic plan for exploratory objectives

8.6.1 The nonparametric Kaplan-Meier method will be used to estimate median RFS.

8.6.2 The nonparametric Kaplan-Meier method will be used to estimate median OS.

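### RFS as defined does not count death without recurrence and has no censoring rule, so it would read too favourably whenever such a death occurs and is censored or ignored

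*Combined protocol and SAP*

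**What the plan says.** RFS is defined identically in 2.4.1 and 8.4.1: "Recurrence-free survival (RFS), defined as time from surgery until evidence of disease recurrence". Section 7.3, which says what counts as recurrence, lists radiologic progression, clinical progression judged by the investigator, and "Death from disease progression". No other death is named.

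The next line of the plan (2.4.2 and 8.4.2) treats OS differently: "Overall survival (OS), defined as time from surgery until death from any cause or last follow-up".

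The analysis is stated in 8.6.1: "The nonparametric Kaplan-Meier method will be used to estimate median RFS". Nothing is said about when a patient without recurrence is censored, or how a death without recurrence is handled.

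The label also varies. Sections 2.2.1 and 8.2.1 abbreviate median recurrence-free survival as mPFS, which the glossary expands as "Median progression-free survival". The synopsis uses mRFS for the same quantity.

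**The concern.** The name of the endpoint says survival without recurrence, but its definition measures time to recurrence. In a phase I trial that adds proton therapy to intensive chemotherapy, a toxic death is the outcome one would least want left out of such an endpoint. Followed literally, the plan would not let that death lower RFS.

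Two analysts could also follow the text and report different RFS medians from the same data. One might count all deaths because of the endpoint's name, and the other only recurrences because of its definition. They could also choose different censoring dates. The synopsis presents the trial as a basis for later designs, so its RFS figure may be carried forward.

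**Working it through.** **1. Definitions side by side**

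| | RFS (2.4.1, 8.4.1, with 7.3) | OS (2.4.2, 8.4.2) |
|---|---|---|
| Event | Recurrence | Death |
| Deaths counted | From progression only | From any cause |
| End of time without event | Not stated | Last follow-up |

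**2. The plan's own figure.** No RFS rate, target or assumed median is stated. The only design figure is the number of patients. Following the 3+3 rules in 8.5 through all branches gives totals of 3, 6, 9 or 12, which reproduces the stated 3-12. The maximum of 12 (six at each level) is used below. The 2-12 in 8.3 fits only if accrual stops once the first two patients both have a DLT.

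**3. Direction.** Kaplan-Meier is S(t) = product of (1 - d/n) over event times, with d events among n at risk. If a death without recurrence is censored, the risk sets do not change, but its factor (1 - 1/n) is replaced by 1. The recurrence-only curve is then never below the all-death curve, and the two are equal if no such death occurs. Simulated 12-patient trials showed no exception.

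A constructed example has 12 patients, with events at 6, 8, 9, 11, 13, 15, 18, 20 and 24 months and censoring at 28, 30 and 30 months.
- All nine counted: S falls to 6/12 = 0.50 at 15 months, so the median is 15.
- If the 6-month event is an uncounted death: S is 6/11 = 0.545 at 15 months and 5/11 = 0.455 at 18, so the median is 18.

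One early death, if counted, lowers the curve by 1/12 = 8.3 points.

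**4. Size, with assumed rates.** Constant hazards are assumed: median time to recurrence 20 months, and other-cause death 1% or 5% per year.
- h1 = ln2/20 = 0.03466 per month
- h2 = 0.01/12 = 0.00083 or 0.05/12 = 0.00417 per month

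| Quantity | Formula | 1%/year | 5%/year |
|---|---|---|---|
| Share of RFS events missed | h2/(h1+h2) | 2.3% | 10.7% |
| True median RFS (months) | ln2/(h1+h2) | 19.53 | 17.854 |
| Overstatement against 20 (months) | difference | 0.47 | 2.146 |
| True 24-month RFS | exp(-24(h1+h2)) | 42.7% | 39.4% |
| Overstatement against exp(-24 h1) = 43.5% | difference, unrounded | 0.9 points | 4.1 points |

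With the assumed recurrence median at 15 months the overstatement is 0.27-1.24 months; at 30 months it is 1.04-4.58 months.

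**5. Chance that the definition matters.** The probability p that one patient dies without recurrence within T months is h2/(h1+h2) x [1 - exp(-T(h1+h2))]. T is 24 months if follow-up is counted from C6D1. If it is counted from EOT, T is up to 24 + 3.2 = 27.2, because C6 in DL1 (28 days) plus cycles 7-11 (5 x 14 days) is 98 days. The wording of 4.4.6 favours EOT.
- 1%/year: p = 1.35-1.45%, so 1 - (1-p)^12 = 15.0-16.1%
- 5%/year: p = 6.5-7.0%, so 1 - (1-p)^12 = 55.4-58.1%

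Over the whole range this is 15-58% with 12 patients. With 6 patients it is about 8-35%, and with 3 about 4-20%.

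**6. Sampling error.** In 400,000 simulated samples of 12 uncensored exponential times with median 20 months, 95% of the sample medians lay between 6.9 and 37.1 months. The upper end would not be seen in practice, because follow-up stops earlier and such medians would be reported as not reached. The spread is still far wider than the shifts in step 4.

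**The case against.** The best defence is that little depends on this endpoint. RFS is exploratory, no dose or safety decision uses it, and there are at most 12 patients. A death without recurrence is not hidden: it counts for OS, enters the death summaries in 8.7.4, and is an SAE under 6.3.2 while events are being collected. All of this stands and sets the severity.

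Several stronger readings are tempting but not supported.

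- *The RFS estimate is certain to be too favourable.* It is so only if a death without recurrence occurs. On the assumed rates, none occurs in 42-85% of 12-patient trials.
- *The error always runs one way.* That holds if the death is censored or ignored while the patient stays in the analysis. If the patient were dropped altogether, the curve before the death could be lower: after one earlier recurrence it would be 10/11 = 90.9% instead of 11/12 = 91.7%. Dropping the patient is the less natural reading, but no rule excludes it. Also, clinical progression in 7.3 includes a need for radiation, chemotherapy or surgery without stating that it must be due to cancer. That could add RFS events.
- *The missing censoring rule makes RFS optimistic.* It has no fixed direction; the harm is that the estimate cannot be reproduced from the plan.
- *Starting the clock at surgery biases RFS and OS.* Patients must reach entry alive and without known recurrence, and those who do not start are substituted (4.2.1, 4.2.1.12). But the stated objective is "To determine, in patients with resected PDAC undergoing PRT integrated within adjuvant FFX", and no comparison with all resected patients is planned. For that population this is a matter of labelling.

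**Conclusion.** The definition is wrong as written, and the point is minor. The text leaves deaths without recurrence out of RFS while the adjacent OS definition counts every death. When such a death occurs and is censored or ignored, RFS is overstated; otherwise there is no bias.

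The illustrative size, about 0.5-2.1 months on the median and 0.9-4.1 points at 24 months, rests on constant hazards, a 20-month recurrence median and 1-5% annual other-cause mortality. None of these comes from the documents. The RP2D and the safety conclusions do not change.

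As a note only: the from-surgery RFS and OS medians describe patients who reached study entry alive and without recurrence, and the report should say so.

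**What to change.** In 2.4.1 and 8.4.1, define RFS as the time from surgery to first recurrence or death from any cause, whichever comes first, with patients alive and without recurrence censored at their last disease assessment. In 2.2.1 and 8.2.1, replace mPFS with mRFS to match the synopsis. Section 7.3 can remain as the definition of recurrence, since the endpoint itself would then bring in all deaths.

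This costs a few lines of text and no new visits: scans and survival status are already scheduled through follow-up in Tables 2 and 3. The one downside is that reported RFS may be slightly less favourable. The change is best made before outcomes are known.
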